9. STUDY DOCUMENTATION, MONITORING, AND ADMINISTRATION

9.1 STUDY DOCUMENTATION

The investigator must maintain adequate and accurate records to enable the conduct of the study to be fully documented, including but not limited to the protocol, protocol amendments, Informed Consent Forms, and documentation of IRB/EC and governmental approval. In addition, at the end of the study, the investigator will receive the patient data, which includes an audit trail containing a complete record of all changes to data.

9.2 PROTOCOL VIOLATIONS

The investigator should document and explain any protocol violations. The investigator should promptly report any violations that might impact patient safety and data integrity to the Sponsor and to the IRB/EC in accordance with established IRB/EC policies and procedures.

9.3 SITE INSPECTIONS

Site visits will be conducted by the Sponsor or an authorized representative for inspection of study data, patients' medical records, and eCRFs. The investigator will permit national and local health authorities, Sponsor monitors, representatives, and collaborators, and the IRBs/ECs to inspect facilities and records relevant to this study.

Alteplase—Genentech, Inc.
64/Protocol ML29093, Version 3

9.4 ADMINISTRATIVE STRUCTURE

Genentech, Inc., is the Sponsor and will have oversight of study management, including project management, oversight of data management, and statistical programming. A CRO will assist with study management, including project management, medical monitoring (as needed), clinical monitoring, data monitoring, and data management. Patients will be enrolled at approximately 75 sites in North America.

The CRO will manage site activation, study drug supply, patient enrollment and tracking, and clinical monitoring. Genentech will handle study drug distribution.

A Steering Committee will provide scientific oversight for this study. The Steering Committee will be composed of Genentech representatives and external advisors. The Steering Committee will perform functions such as:

- Provide recommendations regarding changes in the study conduct
- Review results of the final analyses for primary and secondary endpoints
- Participate in the drafting and publishing of final study results

An iDMC will be responsible for monitoring the overall efficacy and safety of the patients in the trial after treatment with alteplase. The iDMC will be composed of external advisors. The iDMC will perform functions such as:

- Review all accumulated safety data at interim analysis
- Review efficacy data analysis performed for interim analysis for consideration of potential discontinuation of the trial for futility
- Make recommendation to the Sponsor as to if it is appropriate to discontinue the study after assessing the interim efficacy and safety data in aggregate
- Determine if the study should continue after review of interim analysis results

An iDCC will be responsible for the preparation and review of unmasked data.

A central IRB will be utilized when possible to ensure the timely submission and approval of site regulatory documents for sites not required to use a local IRB. The CRO will be responsible for management of the central IRB.

An EDC system will be used to capture data for the study.

An IWRS will be utilized for randomization, patient tracking, and drug inventory management for the study.

9.5 PUBLICATION OF DATA AND PROTECTION OF TRADE SECRETS

Regardless of the outcome of a trial, the Sponsor is dedicated to openly providing information on the trial to healthcare professionals and to the public, both at scientific congresses and in peer-reviewed journals. The Sponsor will comply with all

Alteplase—Genentech, Inc.
65/Protocol ML29093, Version 3

requirements for publication of study results. For more information, refer to the Roche Global Policy on Sharing of Clinical Trials Data at the following Web site:

<http://www.rochetrials.com/pdf/RocheGlobalDataSharingPolicy.pdf>

The results of this study may be published or presented at scientific congresses. For all clinical trials in patients involving an IMP for which a marketing authorization application has been filed or approved in any country, the Sponsor aims to submit a journal manuscript reporting primary clinical trial results within 6 months after the availability of the respective clinical study report. In addition, for all clinical trials in patients involving an IMP for which a marketing authorization application has been filed or approved in any country, the Sponsor aims to publish results from analyses of additional endpoints and exploratory data that are clinically meaningful and statistically sound.

The investigator must agree to submit all manuscripts or abstracts to the Sponsor prior to submission for publication or presentation. This allows the Sponsor to protect proprietary information and to provide comments based on information from other studies that may not yet be available to the investigator.

In accordance with standard editorial and ethical practice, the Sponsor will generally support publication of multicenter trials only in their entirety and not as individual center data. In this case, a coordinating investigator will be designated by mutual agreement.

Authorship will be determined by mutual agreement and in line with International Committee of Medical Journal Editors authorship requirements. Any formal publication of the study in which contribution of Sponsor personnel exceeded that of conventional monitoring will be considered as a joint publication by the investigator and the appropriate Sponsor personnel.

Any inventions and resulting patents, improvements, and/or know-how originating from the use of data from this study will become and remain the exclusive and unburdened property of the Sponsor, except where agreed otherwise.

9.6 PROTOCOL AMENDMENTS

Any protocol amendments will be prepared by the Sponsor. Protocol amendments will be submitted to the IRB/EC and to regulatory authorities in accordance with local regulatory requirements.

Approval must be obtained from the IRB/EC and regulatory authorities (as locally required) before implementation of any changes, except for changes necessary to eliminate an immediate hazard to patients or changes that involve logistical or administrative aspects only (e.g., change in Medical Monitor or contact information).

Alteplase—Genentech, Inc.
66/Protocol ML29093, Version 3

Appendix 1 (cont.) Schedule of Assessments

ASSESSMENTS	Screening and Baseline (Visit 1)	Study Drug Administration	22–36 Hours from Start of Study Drug Administration (Visit 2)	Day 5 (or Discharge if Sooner) (Visit 3)	30 Days (± 7 Days) Phone Call (Visit 4)	90 (± 14) Days/Study Completion (Visit 5)	Early Discontinuation (Phone call, if possible)
Discharge location				X			X
Patient survival					X	X	X
mRS ^j					X	X	
GOS						X	
BI ^k						X	
EQ-5D ^k						X	
CES-D ^k						X	
SIS-16 ^k						X	
Cognitive assessments ^l						X	
Walking speed ^m						X	
Concomitant medications ⁿ	X		X	X	X	X	X
Assessment of pregnancy					X		
Adverse event ^o		X	X	X	X	X	X

BI=Barthel Index; BNT=Boston Naming Test; CES-D=Centers for Epidemiologic Studies, Depression; CT=computed tomography; DW MRI=diffusion-weighted MRI; European Quality of Life=EQ-5D; FLAIR=fluid-attenuated inversion recovery; GOS=Glasgow Outcome Scale; GRE=gradient echo; HVLT-R=Hopkins Verbal Learning Test-Revised; ICH=intracranial hemorrhage; INR=international normalized ratio; MRI=magnetic resonance imaging; mRS modified Rankin Scale; NIHSS=NIH Stroke Scale; Stroke Impact Scale-16=SIS-16; SW MRI=susceptibility-weighted MRI; WAIS III=Wechsler Adult Intelligence Scale III.

Alteplase—Genentech, Inc.
71/Protocol ML29093, Version 3

Appendix 1 (cont.) Schedule of Assessments

- ^a Includes smoking history and stroke history.
- ^b A partial neurological examination is to be performed for each patient. The NIHSS will be a component of the neurological examination and will be performed only by practitioners who are certified to perform an NIHSS assessment. Additional, or supplemental, neurological exams will also be performed, including assessment of mental status, cranial nerves, motor function and coordination.
- ^c Includes pulse and systolic/diastolic blood pressure (while patient is in a supine position). *Record abnormalities on the Adverse Event eCRF.*
- ^d Complete blood count includes hemoglobin, hematocrit, white blood cell count, and platelet count.
- ^e Coagulation status includes INR values of >1.7, activated partial thromboplastin time, patient or family report of patient currently taking an oral anticoagulant (e.g., dabigatran, rivaroxaban, apixaban, edoxaban), or patient or family report of patient currently taking a low-molecular-weight heparin (e.g., dalteparin, enoxaparin) within the last 48 hours.
- ^f Pregnancy status will be determined in women of childbearing potential. Serum or urine pregnancy test can be collected.
- ^g Serum glucose (values of <50 mg/dL are contraindicated for alteplase).
- ^h MRI or CT scan should be performed if any clinical findings suggest ICH.
- ⁱ NIHSS score should be assessed and recorded at the time of any clinical findings that suggest ICH.
- ^j The mRS may be performed by telephone, if necessary, for visits on Days 30 and 90.
- ^k The BI, CES-D, EQ-5D, and SIS-16 can be administered by phone interview if an in-person patient visit cannot be scheduled in the allotted time.
- ^l Assessments include: Controlled Oral Word Association test; HVLT-R trials 1, 2, and 3; digit symbol coding from the WAIS III; Forward and Backward Digit Span test; Benton Judgment of Line Orientation, form V; HVLT-R trial 4 and recognition; semantic fluency (Animal Naming test); and BNT (15-item short form).
- ^m Assessment of walking speed requires an in-person patient visit and is best combined with administration of the BI, CES-D, EQ-5D, and SIS-16.
- ⁿ Concomitant medications include any prescription medications or over-the-counter preparations used by the patient within 7 days prior to screening.
- ^o Adverse event assessments will be performed during study drug administration; at 22–36 hours after study drug administration; on Days 5, 30, and 90 (may be done via telephone interview if necessary), and at early discontinuation. Refer to Section 5.3.1 (Adverse Event Reporting Period) for further details.

Appendix 2

Alteplase Administration

Administration of bolus

Step 1:

Inspect solution

After reconstitution to 1 mg/mL, inspect solution for particulate matter and discoloration prior to administration

Step 2:

Discard excess

To ensure proper dosing, discard excess by removing from vial any quantity of drug in excess of that specified for patient treatment. When drawing off excess solution, be sure to insert the needle into the peripheral area of the vial top, away from the puncture site caused by the transfer device

Step 3:

Prepare bolus

Withdraw 10% of the 0.9-mg/kg dose in one of the following ways:

- Remove from vial using a syringe and needle,
- Remove from port (second injection site) on infusion line after infusion set is primed, or
- Program infusion pump to deliver bolus at infusion initiation

Step 4:

Administer bolus

Administer initial IV bolus over 1 minute

Administration of remainder of dose

Infuse the remaining 90% of 0.9-mg/kg dose over 60 minutes.

50-mg vials—Administer using either a polyvinyl chloride bag or glass vial and infusion set.

No medication should be added to the infusion solutions that contain alteplase.

For specifics regarding dosing and administration, please see the [Activase full Prescribing Information](#).

Alteplase—Genentech, Inc.
73/Protocol ML29093, Version 3

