4.1.2 Exclusion Criteria

Patients who meet any of the following criteria will be excluded from study entry:

- CT or MRI findings consisting of one of the following:
 - CT with clear large hypodensity that is greater than one-third middle cerebral artery (MCA) territory (or greater than 100 cc if not in MCA territory),
 - MRI with clear large hyperintensity on concurrent diffusion-weighted (DW) and fluid-attenuated inversion recovery (FLAIR) that is greater than one-third MCA territory (or greater than 100 cc if not in MCA territory),
 - Imaging lesion consistent with acute hemorrhage of any degree, OR
 - Evidence of intraparenchymal tumor
- Disability prior to the presenting stroke (historical mRS score ≥ 2)
- Standard contraindications to IV alteplase for patients treated within 3 hours of symptom onset, including:
 - Head trauma or previous stroke within the previous 3 months
 - Myocardial infarction within the previous 3 months
 - Gastrointestinal or urinary tract hemorrhage within the previous 21 days
 - Major surgery within the previous 14 days
 - Arterial puncture at a non-compressible site within the previous 7 days
 - Any history of ICH with the exception of <5 chronic microbleeds on MRI
 - Elevated blood pressure (systolic >185 mm Hg or diastolic >110 mm Hg), or the use of aggressive measures (use of more than two intravenous agents to lower blood pressure) to achieve blood pressure within acceptable parameters
 - Treatment with unfractionated heparin within the last 48 hours and activated partial thromboplastin time (aPTT) outside of the normal range as specified by the center's local laboratory
 - Blood glucose <50 mg/dL
 - International normalized ratio (INR) >1.7 (Note: This does not need to be verified prior to randomization if there is no clinical suspicion of abnormality.)
 - Platelet count of $<100,000/\text{mm}^3$ (Note: This does not need to be verified prior to randomization if there is no clinical suspicion of abnormality.)
 - Treatment with a direct thrombin inhibitor or factor Xa inhibitor (including novel oral anticoagulants [e.g., dabigatran, rivaroxaban, apixaban, edoxaban]) within the last 48 hours
 - Treatment with a low-molecular-weight heparin (e.g., dalteparin, enoxaparin) within the last 48 hours
- Allergic reactions to study drug, aspirin, *or* nonsteroidal anti-inflammatory drugs (NSAIDs)

Alteplase—Genentech, Inc.
33/Protocol ML29093, Version 3

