4.6 TIMING OF STUDY ASSESSMENTS

4.6.1 Screening/Baseline (Visit 1)

The following standard of care assessments performed prior to obtaining informed consent will be used in the screening process. Once consent is obtained, the results of the standard of care assessments may be used for the study.

- Medical history
- Demographics
- Neurological examination
- Vital signs
- Complete blood count without differential
- Coagulation status
- Pregnancy test (serum or urine)
- Serum blood glucose
- Non-contrast CT scan or MRI, including DW MRI, either SW or GRE, and FLAIR images
- NIHSS score (Note: This must be performed by an NIHSS-certified practitioner; see [Appendix 7](#))
- Concomitant medications

All screening evaluations with the exception of certain laboratory results (e.g., coagulation and complete blood count) must be completed and reviewed to confirm that patients have met all eligibility criteria prior to treatment. Serum glucose is required to confirm eligibility prior to enrollment; however, if the investigator feels there is clinical suspicion that would be related to an exclusion laboratory test that would preclude the patient from eligibility, the results of those laboratory tests must be obtained prior to treatment.

The investigator will maintain a screening log to record details of all patients consented to confirm eligibility or record reasons for screening failure, as applicable.

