4.6.5 Visit 5 (Day 90 [± 14 Days])/Study Completion)

Primary and secondary efficacy endpoints, as well as all exploratory endpoints, will be assessed at Day 90 with the patient. The following assessments will be performed:

- NIHSS score ([Appendix 7](#))
- Patient survival
- mRS ([Appendix 8](#))
- GOS ([Appendix 9](#))
- BI ([Appendix 10](#))
- EQ-5D ([Appendix 4](#))
- SIS-16 ([Appendix 5](#))
- CES-D ([Appendix 6](#))
- Cognitive assessments ([Appendix 11](#))
 - Controlled Oral Word Association test
 - HVLT-R trials 1, 2, and 3
 - Digit symbol coding from the WAIS III
 - Forward and Backward Digit Span test
 - Benton Judgment of Line Orientation test, form V
 - HVLT-R trial 4 and recognition
 - Animal Naming test

¹ AE/SAE collection should be started as soon as study drug administration (bolus) is initiated.

- BNT 15-item short form

The above cognitive assessments will be provided in Spanish for those patients requiring translations with the exception of the BNT 15-item short form.

- Walking speed ([Appendix 12](#))
- Concomitant medications
- SAEs and certain AEs (See Section [5.3.1](#))

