5.3.1 Adverse Event Reporting Period

Investigators will seek information on AEs at each patient contact. All AEs, whether reported by the patient or noted by study personnel, will be recorded in the patient’s medical record and on the Adverse Event eCRF.

After initiation of study drug, all AEs (including serious and non-serious AEs), regardless of relationship to study drug, will be reported until 30 days after administration of study drug.

After 30 days until 90 days after administration of study drug, the following AEs should be recorded on the AE CRF:

- All SAEs
- Non-serious ICHs
- Non-serious AESIs
- All AEs that resulted in withdrawal from the study

All SAEs and non-serious AESIs require immediate reporting to the Sponsor (see Section 5.4).

After 90 days, the investigator is not required to actively monitor patients for AEs; however, the Sponsor should be notified if the investigator becomes aware of any post-study SAEs (see Section 5.6).

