5.3.3.5 Abnormal Vital Sign Values

Not every vital sign abnormality qualifies as an AE. A vital sign result must be reported as an AE if it meets any of the following criteria:

- Is accompanied by clinical symptoms
- Results in a change in study treatment (e.g., dosage modification, treatment interruption, or treatment discontinuation)
- Results in a medical intervention or a change in concomitant therapy
- Is clinically significant in the investigator's judgment

It is the investigator's responsibility to review all vital sign findings. Medical and scientific judgment should be exercised in deciding whether an isolated vital sign abnormality should be classified as an AE.

If a clinically significant vital sign abnormality is a sign of a disease or syndrome (e.g., high blood pressure), only the diagnosis (i.e., hypertension) should be recorded on the Adverse Event eCRF.

Observations of the same clinically significant vital sign abnormality from visit to visit should *only* be recorded *once* on the Adverse Event eCRF (see Section 5.3.3.3 for details on recording persistent AEs).

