5.3.3.7 Preexisting Medical Conditions

A preexisting medical condition is one that is present at the screening visit for this study. Such conditions should be recorded on the General Medical History and Baseline Conditions eCRF.

A preexisting medical condition should be recorded as an AE only if the frequency, severity, or character of the condition worsens during the study. When recording such events on the Adverse Event eCRF, it is important to convey the concept that the preexisting condition has changed by including applicable descriptors (e.g., more frequent headaches").

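### Schedule footnote c sends vital-sign abnormalities to the Adverse Event form, although the only scheduled vital signs are taken before dosing, when adverse event collection has not begun.

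*Protocol*

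**What the plan says.** Footnote c of Appendix 1 defines vital signs as pulse and supine blood pressure and then adds: "Record abnormalities on the Adverse Event eCRF". It sets no limit by time of measurement, clinical significance or change from baseline. In the schedule grid the vital-signs row has one mark, under Screening and Baseline (Visit 1). Section 4.6.1 includes vital signs in a list introduced by "The following standard of care assessments performed prior to obtaining informed consent will be used in the screening process". Sections 4.6.2 to 4.6.6, which cover the later visits and early discontinuation, do not list them.

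Other current text on the same matter reads differently:

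- Section 4.6, footnote 1: "AE/SAE collection should be started as soon as study drug administration (bolus) is initiated".
- Section 5.3.1: "After initiation of study drug, all AEs (including serious and non-serious AEs), regardless of relationship to study drug, will be reported until 30 days".
- Appendix 1, AE row: no mark at Visit 1. Footnote o begins: "Adverse event assessments will be performed during study drug administration".
- Section 5.3.3.5: "Not every vital sign abnormality qualifies as an AE". A list of qualifying criteria follows.
- Section 5.3.3.7, on conditions present at screening: "Such conditions should be recorded on the General Medical History and Baseline Conditions eCRF". They become AEs only if they worsen during the study.

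**The concern.** A site cannot follow footnote c and the Section 5 rules together for the one set of vital signs the protocol schedules. The footnote is an instruction about which form to use. If it is obeyed, findings that existed before treatment enter the AE data, and the incidence, severity and spectrum of AEs is a stated safety outcome (Section 3.5.2).

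The situation will arise in practice. The blood pressure exclusion, "Elevated blood pressure (systolic >185 mm Hg or diastolic >110 mm Hg", leaves patients with raised pressures below those limits eligible, so abnormal baseline values can occur in enrolled patients. The footnote does not define an abnormality and, unlike footnote o, does not point the reader to Section 5.

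At stake is the cleanness of the descriptive AE tables. Records unrelated to treatment would raise the rates in both arms, and their number would vary with each site's reading of the conflict.

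**Working it through.** No arithmetic applies, because the point rests on no sample size, error rate or event count. The check is to set the current Version 3 passages side by side.

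1. **Which measurements does footnote c govern?** It is attached to the vital-signs row. Scheduled vital-sign assessments before dosing: 1 (Visit 1). Scheduled at or after dosing: 0. Section 4.6.1 places that one assessment in the standard-of-care screening work done before consent, and the bolus comes only after consent is signed (Section 4.2).

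2. **When does AE collection begin?** Section 4.6 footnote 1, Section 5.3.1, the AE row and footnote o all put the start at study drug administration. Every scheduled measurement under footnote c therefore falls outside the collection period.

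3. **Would a baseline abnormality qualify on its content?** Section 5.3.3.5 admits only abnormalities that are accompanied by symptoms, change study treatment, lead to an intervention or a change in concomitant therapy, or are judged clinically significant. Footnote c applies no such test.

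4. **Where does a condition present at screening belong?** Section 5.3.3.7 names the General Medical History and Baseline Conditions form. Footnote c names a different form for the same finding.

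5. **Can such a record be completed sensibly?** Section 5.3 requires a causality assessment for each AE, but at this point no study drug has been given. Grades 1 and 2 for hypertension in Appendix 14 refer to a change of more than 20 mm, which a single pre-dose reading cannot show.

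6. **Is the sentence a leftover or a deliberate change?** Footnote c in Version 2 does not contain it. Version 2 had already moved the start of AE collection from screening to study drug administration. The Version 3 summary of changes attributes the schedule revision to template language. Template wording suited to a study with on-treatment vital signs seems to have been attached to a baseline-only row. That is an inference; the contradiction does not depend on it.

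**The case against.** The strongest reply is that one footnote sentence stands against several consistent rules. Section 5.2.1 ties an AE to a patient who has been given a product, Section 5.3.1 starts reporting at study drug initiation, and Sections 5.3.3.5 and 5.3.3.7 narrow what counts. A careful site would follow Section 5 and make no pre-dose entries. The sentence can also be read as only naming the form to use once an abnormality qualifies, or as aimed at vital signs taken in routine care after dosing.

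Much of this stands. It means that entry of pre-dose findings is a possibility, not a certainty. It does not remove the conflict: the sentence carries no qualifier, and the only scheduled measurement in its row is the one before dosing.

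A reader might go further and infer that pre-treatment findings will be counted in the reported AE rates because Section 6.3 states no restriction to onset after dosing. The document does not support that. Such a restriction is commonly left to the statistical analysis plan, which is not at hand, and AE reports carry a starting date (Section 5.3.3.1) by which pre-dose entries could be identified. A reader might also want a figure for the dilution of between-arm ratios. The protocol gives neither a frequency of abnormal baseline values nor an expected AE rate, so any figure would rest on invented inputs.

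**Conclusion.** The contradiction is real and lies in current text: footnote c is wrong as written. Its consequence is limited. Sites that follow it could record pre-treatment pulse and blood pressure findings as AEs, which would inflate descriptive AE incidence in both arms and make it depend on site interpretation. The size cannot be derived from the protocol.

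Three things bound the harm. General AEs are only described (Section 6.3). The outcomes compared by Fisher's exact test (symptomatic intracranial hemorrhage, any intracranial hemorrhage, overall mortality, and stroke-related and neurological deaths) do not draw on these entries. Assignment is randomized and stratified by site, so pre-dose findings and local recording habits should balance between arms in expectation and favour neither.

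The conclusion assumes that at least some sites apply the footnote literally. Whether the entries would reach the reported tables depends also on the onset rule in the statistical analysis plan.

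**What to change.** Delete the last sentence of footnote c. Alternatively, replace it with wording to this effect: abnormal values at Screening/Baseline are recorded on the General Medical History and Baseline Conditions form, and a vital-sign abnormality goes on the Adverse Event form only if it starts or worsens after the bolus and meets Section 5.3.3.5. A cross-reference to Sections 5.3.1 and 5.3.3.5, as footnote o already gives to Section 5.3.1, would keep the schedule and the body text aligned. The form completion guideline should say the same.

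The cost is one footnote edit and a guideline note. No assessment or analysis changes, and sites have fewer records to enter and assess.
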